4.9. Safety Analyses

Safety analyses will be conducted using the Safety Population.

4.9.1. Adverse Events

Adverse events will be coded using the Medical Dictionary for Regulatory Activities (MedDRA) and displayed in tables and listings using System/Organ/Class (SOC) and Preferred Term.

Analyses of adverse events will be performed for those events that are considered treatment emergent, where treatment emergent is defined as any adverse event with onset after the administration of study medication through the end of the study, i.e. 30 days after the surgery or any event that was present at baseline but worsened in intensity or was subsequently considered drug-related by the investigator through the end of the study.

Adverse events are summarized by subject incidence rates, therefore, in any tabulation, a subject contributes only once to the count for a given adverse event (SOC or preferred term).

The number and percentage of subjects with any treatment-emergent adverse event, with any treatment-emergent adverse events assessed by the Investigator as related to treatment (definite, probable, or possible relationship), and with any serious adverse event will be summarized by treatment group and overall. In these tabulations, each subject will contribute only once (i.e., the most related occurrence or the most intense occurrence) to each of the incidence rates in the descriptive analysis, regardless of the number of episodes.

No formal hypothesis-testing analysis of adverse events incidence rates will be performed.

All adverse events occurring on study will be listed in subject data listings.

By-subject listings also will be provided for the following: subject deaths; serious adverse events; and adverse events leading to withdrawal.

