1 PROTOCOL SUMMARY

1.1 SYNOPSIS

Title	Pharyngeal Electrical Stimulation Evaluation
	for D ysphagia after Stroke (PhEED)
Study Description	This is a randomized, sham-controlled, patient masked,
	outcome assessor-blinded study to assess a Pharyngeal
	Electrical Stimulation (PES) Catheter for treatment of
	oropharyngeal dysphagia following a stroke. The main clinical
	outcomes will be measured by videofluoroscopic swallowing
	study (VFSS) and bedside swallowing assessments at 48
	hours. Randomization will use stratification based on site and
	baseline PAS. Minimization may also be included to ensure

CONFIDENTIAL Page 8 of 71

group balance for study site and additional baseline covariates. All patients will have the Phagenyx® Catheter placed prior to randomization, and will receive either an active treatment of Pharyngeal Electrical Stimulation (PES) or a sham treatment performed by a healthcare professional (HCP) that is unblinded to treatment assignment. All other speech pathology standard dysphagia care will be provided by a speech language pathologist (SLP) that is blinded to treatment assignment. Administration of all protocol-specific assessments will be conducted by personnel blinded to treatment assignment.

The study will follow an adaptive group sequential design with unblinded sample size re-assessment. To ensure 180 evaluable patients with 7-day data and assuming a 20% dropout rate, 225 patients will be enrolled initially. An interim analysis for futility will occur after the first 60 patients complete their 7-day visits and another interim analysis will be performed for efficacy and futility after 120 patients complete their 7-day visits. The total sample size may be increased up to 338 patients after the second interim analysis to ensure up to 270 evaluable patients. Up to 15 investigational centers across the US and Europe will participate in this study. The enrollment period is expected to be approximately 24 months and patient participation will last for approximately 11 weeks. Patients will be assessed at the following intervals: baseline, 48 hours, 7 14 days or at discharge, whichever is first, and 11 weeks after completion of the study treatments.

Study Objectives

Primary Objective: To evaluate the efficacy of Phagenyx® treatment in reducing the severity of unsafe swallows.

Secondary Objective: To evaluate the efficacy of Phagenyx® treatment in improving nutritional management.

Exploratory Objectives:

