Patients will be exposed to the inherent risks associated with placement of any NGT, and patients who receive nutrition orally or via PEG will be exposed to additional risks of requiring the nasogastric Phagenyx® Catheter remain in place for the time required to complete the three consecutive daily stimulation sessions. Patients who participate at sites that utilize NGTs for feeding may have the Phagenyx® Catheter indwelling for longer than the time required to administer study treatment and therefore may be exposed to incremental risks associated with the design of the Phagenyx® Catheter incorporating embedded electrodes.

Nasogastric tube feeding is common practice and thousands of tubes are inserted daily without incident. However, there is a risk that the tube may become misplaced into the lungs ¹⁷ during insertion, or move out of the stomach at a later stage. The actual incidence of complications related to NGT placement is very low. Sparks et al., performed a meta-analysis which demonstrated the potential severity of pulmonary complications as well as the rare incidence in which they occur: pneumothorax and subsequent death occurred in 0.35% and 0.05% cases of nasoenteral tube (NET) placement, respectively¹⁸.

The risk of accidental enteral feeding into the airway following misplacing a nasogastric tube is rarely mentioned in published literature. However, the United Kingdom National Patient Safety Agency issued a National Safety Alert in 2011 in attempts to raise awareness of this risk and provide guidelines to reduce the risk¹⁸ of feeding into the airway. The alert emphasizes that while "thousands of tubes are inserted daily without incident," grave harm may result in unrecognized misplacement of a nasogastric tube. To mitigate this risk, verification of proper NG tube placement is standard clinical practice and is also part of the instructions for use for placing the Phagenyx® Catheter.

CONFIDENTIAL Page 25 of 71

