The standardized VFSS protocol proposed for use in this study specifies a continuous pulse rate of 30 pps. The patient population exposed to ionizing radiation in this study will be of advanced age, with similar studies enrolling patients with an average age over 70 years. Thus the relative incremental risk associated with study-specific exposure to ionizing radiation is considered minimal based on the stochastic nature of risk associated with ionizing radiation exposure.

Finally, the objective of the VFSS is to assess the degree to which boli of incrementally thicker media penetrate or aspirate into the airway. Hence, the method by which risk of aspiration is studied also imparts an incremental risk of patients developing aspiration pneumonia after performing the VFSS. Jo et. al., recently published a retrospective review of the occurrence of pneumonia developing after aspiration during VFSS at their teaching hospital in Chuncheon, South Korea⁵¹. The authors reviewed 696 VFSS for cases in which blood cultures were performed within 3 days following the VFSS due to newly developed infectious signs. Pneumonia was suspected when there was some evidence of respiratory infectious signs in clinical, radiological, and laboratory findings. Fifteen cases of pneumonia were identified in this manner. Review of the VFSS procedure records indicated that only seven of these cases (1%) could be attributed to the VFSS.

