8.2.5 EVENT ASSESSMENT AND FOLLOW-UP

All AEs and SAEs will be captured on the AE eCRF. Information to be collected includes event description, date of onset, seriousness, classification of severity and relatedness, treatment, and resolution/stabilization of the event. All AEs/SAEs occurring while on study must be documented appropriately regardless of relationship. Adverse events/SAEs will be collected from the time of signing the ICF through the patient's study termination and will be assessed for at each encounter with the patient. Adverse events may be reported by patients, elicited through questioning by an Investigator or designee, or collected via observation by the Investigator. In addition, patients will be instructed to contact the investigator and/or study coordinator if any significant adverse events occur between study evaluation visits.

Any medical condition that is present at the time that the patient is screened will be considered as baseline and not reported as an AE. However, if the patient's condition deteriorates at any time during the study, it will be recorded as an AE.

CONFIDENTIAL Page 54 of 71

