3. SUBJECT POPULATIONS

3.1. Population Definitions

The following subject populations will be evaluated and used for presentation and analysis of the data:

- The Roll-In (RI) population will consist of all patients enrolled in a non-blinded roll-in manner and remained eligible to receive the Phagenyx treatment after initial pre-procedural VFSS testing is completed and the PAS is determined to meet entry criterion and no exclusions are found. All patients in whom treatment was attempted, regardless of procedural outcome, will be included in this analysis set.
- The **Safety Population** will consist of all patients that were enrolled in the study (including Roll-In patients) and underwent the pre-procedural VFSS with or without subsequent placement of the Phagenyx Catheter.
- The **Intent to Treat (ITT)** Population will consist of all patients that were randomized, irrespective of their protocol adherence and continued participation in the study.
- The **Per Protocol (PP) Population** will consist of all randomized patients who completed the full Phagenyx treatment regimen according to their randomization assignment and for whom completed primary endpoint data are also complete.

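### SAP 4.9.1 starts the adverse-event window at the first treatment, so non-serious placement and baseline-VFSS injuries that resolve before session 1 miss the incidence tables, and the roll-ins' table column is not defined

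*SAP*

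**What the plan says.** **Window.** SAP 4.9.1 opens with a restriction: "Analyses of adverse events will be performed for those events that are considered treatment emergent". It continues: "treatment emergent is defined as any adverse event with onset after the administration of study medication through the end of the study". A second limb adds "any event that was present at baseline but worsened in intensity or was subsequently considered drug-related by the investigator". The section then counts patients with any treatment-emergent AE, any related treatment-emergent AE, and any serious AE, by treatment group and overall. The serious-AE item carries no treatment-emergent qualifier. All on-study AEs are listed, and no formal test is planned.

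**Timing.** Protocol 1.1 states: "All patients will have the Phagenyx® Catheter placed prior to randomization". Protocol 8.2.5 states: "Adverse events/SAEs will be collected from the time of signing the ICF through the patient's study termination".

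**Population.** SAP 4.9 uses the Safety Population. SAP 3.1 defines it as enrolled patients, with this qualification: "including Roll-In patients) and underwent the pre-procedural VFSS with or without subsequent placement of the Phagenyx Catheter". Protocol 9.3 has the same starting point but does not mention roll-ins.

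**Protocol counterpart.** Protocol 9.4.4 summarizes AEs with no treatment-emergent restriction. SAP section 5 says that nothing differs from the protocol.

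**Roll-ins.** Under Protocol 4.1, each US site treats up to three roll-ins, all unblinded and all active. European sites do so by agreement. Both documents keep roll-ins apart from the primary analysis population, but neither says where they appear in the AE tables.

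**The concern.** Three clocks start at different times. AE collection starts at consent, the safety denominator starts at the baseline VFSS, and the tabulated events start at the first session. Catheter placement and the baseline VFSS fall between the second and third. Protocol 8.2.3.3 lists epistaxis, bleeding, pneumothorax and aspiration pneumonia among the events anticipated with the system and its procedures, and Protocol 2.4.1 discusses several of them.

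The matter is about absolute risk. Sham patients also receive the catheter (Protocol 4.2), so a PES-versus-sham contrast cannot show what placement costs. The incidence from placement onward is the main tabular evidence on that hazard, in a trial meant to support a de novo submission, and a listing gives no rate.

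The denominator adds a smaller problem. A patient who never starts a session cannot have an event with onset after treatment, yet counts in the overall column. Roll-ins join the same population with no rule for their column.

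**Working it through.** **Step 1. Order of events.** Consent (collection starts), baseline VFSS (Safety Population starts), catheter placement, randomization, session 1 (table window starts). Protocol 6.1.1 requires the baseline criteria to be met before placement, and Protocol 1.1 puts placement before randomization.

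**Step 2. Each class of event under SAP 4.9.1**, reading baseline as in SAP 4.3.1 (the last measurement before treatment):

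- Non-serious, begins and resolves before session 1: onset is too early and the event is not present at baseline. Listed, not tabulated.
- Non-serious, still present at session 1: tabulated only if it worsens or is judged drug-related. Protocol 8.2.3.2 rates relation to the device or procedure, so the limb's wording does not match the data collected.
- Serious, before session 1: the serious-AE item would admit it, while the section's opening sentence would exclude it. Ambiguous.
- Onset after session 1, including after the 48-hour VFSS: not excluded by the start of the window.

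**Step 3. Reproduce the plan's figures.** Enrollment = evaluable / (1 − dropout): 180 / 0.80 = 225, and 270 / 0.80 = 337.5, rounded up to 338. Both match. The cited VFSS review gives 7 / 696 = 1.01%, matching the stated 1%.

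**Step 4. Expected events.** Protocol 2.4.1 gives the placement rate, "pneumothorax and subsequent death occurred in 0.35% and 0.05% cases of nasoenteral tube (NET) placement", and the VFSS rate, "only seven of these cases (1%) could be attributed to the VFSS". Expected count = N × rate; P(at least one) = 1 − (1 − rate)^N. One placement and one baseline VFSS per patient are assumed, with roll-ins not counted.

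- Pneumothorax: 225 × 0.0035 = 0.79 (P = 55%); 338 × 0.0035 = 1.18 (P = 69%).
- VFSS-attributed pneumonia: 225 × 7/696 = 2.26 (P = 90%); 338 × 7/696 = 3.40 (P = 97%).

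The pneumonia counts are ceilings, because an onset after session 1 is already in the window. The documents do not allow the excluded share to be derived. They also give no rate for the transient minor injuries that are most clearly lost.

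**Step 5. Roll-in share if pooled into PES.** Share = R / (N/2 + R), with 1:1 allocation assumed because the ratio is not stated. R = 8 is one roll-in at each of 8 US sites (the smallest majority of 15), R = 24 is three at each of those 8, and R = 45 is three at all 15 sites.

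| Roll-ins R | N = 225 | N = 338 |
|---|---|---|
| 8 | 8/120.5 = 6.6% | 8/177 = 4.5% |
| 24 | 24/136.5 = 17.6% | 24/193 = 12.4% |
| 45 | 45/157.5 = 28.6% | 45/214 = 21.0% |

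If the roll-in AE rate differed by an assumed 10 points from that of randomized PES patients, the column would move by 10 × share: 0.5 to 2.9 points.

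**The case against.** A reader might infer that catheter and VFSS injuries vanish from the report. They do not. Every AE is listed, a serious event may reach the serious-AE row, and an injury still present at session 1 can count if it worsens or is judged related. Later catheter injuries and events after the follow-up VFSS are not excluded by the start of the window. Pneumothorax, the one placement injury with a cited rate, amounts to about one case and may well be serious. All of this stands, and it narrows the loss to non-serious events that begin and resolve before session 1, plus non-serious events still present that neither worsen nor are judged related.

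It can also be said that both arms receive the catheter before randomization, so the omission does not distort PES versus sham, and that AE rates are descriptive. That stands too, but it does not answer the point about absolute risk.

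On the denominator, it would be wrong to say that untreated patients have no treatment group. Protocol 7.2 provides for patients who are randomized but not treated, and they have an assigned arm. Only patients never randomized lack one, and the documents do not say how many there would be.

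**Conclusion.** The point holds in limited form. Followed as written, SAP 4.9.1 drops a defined class of placement and baseline-VFSS injuries from the incidence tables. This is a wrong rule rather than a missing detail, and it departs from Protocol 9.4.4 without being declared. Absolute device and procedure risk is understated, by an amount the documents do not fix. The counts in Step 4 show the scale of the events at issue, not the number lost; they assume that the protocol's cited rates apply to this population.

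A reader might go further and infer that the by-arm AE comparison is not randomized. The documents do not support that. SAP 3.1 puts roll-ins in the Safety Population, but nothing places them in the PES column; they could have their own column or count only under the overall total. Their separation from the primary analysis population does not settle the AE tables either way. The 4.5% to 28.6% range is therefore conditional on pooling, on 1:1 allocation and on 8 to 45 roll-ins. The top value needs three roll-ins at all 15 sites. The shift of 0.5 to 2.9 points also rests on an assumed rate difference.

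**What to change.** In SAP 4.9.1:

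- Start the AE window at the baseline VFSS or catheter placement, and replace the medication and drug wording with device and procedure wording. The reference in the same sentence to 30 days after surgery also has to be reconciled with a study that has no surgery and follows patients for 11 weeks.
- Tabulate events before session 1 in one pooled table, with two denominators: patients who had the VFSS and patients with a placement attempt.
- State whether the serious-AE row includes events before session 1.
- Base the by-arm AE tables on randomized patients who started an active or sham session, and show roll-ins in their own column.

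Record in SAP section 5 any difference from Protocol 9.3 and 9.4.4 that remains.

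The cost is SAP wording and one extra table. No new data are needed, since AEs are collected from consent. The overall AE rate will look slightly less favourable.

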Roll-in patients will be analyzed independently from the primary analysis population but will not contribute to the sample size cap.

Dysphagic patients enrolled into the study will continue to receive enteral or oral nutrition via the same manner as prior to study entry and will also have the Phagenyx® Catheter placed as part of the study. In the US, patients may receive feeding through the Phagenyx® Catheter for up to 2 weeks as needed. In Europe, patients may receive feeding through the Phagenyx Catheter for up to 30 days.

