5.4 STRATEGIES FOR RECRUITMENT AND RETENTION

Patients will be screened and recruited by the investigators and/or coordinators at each site. Eligible patients could be in an inpatient rehabilitation center, having been transferred from the acute care facility in which they had been initially treated for the stroke, or site standard unit for post-acute stroke patients. The length of stay for these patients should be for up to 2 weeks to complete the study requirements for treatment and 14 day (+/- 1 day) follow up.

Stroke patients identified as dysphagic by clinical bedside assessments between the ages of 18 and 90 years, will be screened for study enrollment. The patient or their legal guardian will be eligible to sign the ICF after the study team explains the study and the patient and family have time to read and understand as well as ask all questions. The importance of study compliance will be emphasized throughout the informed consent process.

The length of study participation is approximately 11 weeks, including post treatment follow-up visits at 48 hours (+/- 24 hrs), 7 days (+/- 1 day), 14 days (+/- 1 day) or discharge, whichever is first, and 11 weeks (+/- 1 week).

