8.1.10 PNEUMONIA ASSESSMENT

A standardized assessment for clinical signs and symptoms associated with pneumonia will be performed over the initial two weeks that patients are enrolled in the study (e.g., baseline through the 14 days or discharge, whichever is first, follow-up. Diagnostic methods are not specified; instead, signs, symptoms, and/or diagnostics test results will be collected on a regular basis (i.e., baseline and post treatment at 48 hours and on days 7, 14 days or discharge, whichever is first, to determine if a standardized diagnosis of pneumonia can be made. Information will be obtained via the patient's medical record

CONFIDENTIAL Page 49 of 71

and recorded on the eCRF. A diagnosis of pneumonia must meet the following set of criteria:

Temperature:

- a) ≥ 37.5°C or higher on two consecutive measurements or
- b) ≥38.0°C or higher (only need one measurement)

AND

Respiration:

- a) rate ≥ 20 breaths/min or
- b) cough AND breathlessness or
- c) purulent sputum *or*
- d) need for oxygen or increase in oxygen flow rate

AND

- a) WBC count $\geq 11.0 \times 10^9$ /L or
- b) Chest infiltrates on radiograph or
- c) Positive sputum culture on microbiology or
- d) Positive blood culture

AND

No other obvious source of infection

If a diagnosis of pneumonia is made, it will be recorded on the AE eCRF and reported as an AE/SAE in accordance with Section 8.2, below.

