2.5. Study Procedures

The schedule of assessments, as outlined in the study protocol, is provided in **Error! Reference source not found.**

 Table 1
 Schedule of Assessments

	Screening	Baseline	Phagenyx Treatment (10 minutes per day, 3 consecutive days)	48±24 Hour Follow- up	7±1 Days Follow- up	14-±1 days or discharge, whichever is first	11±1 Weeks Follow- up	
				Follow-up timing is based on last Phagenyx treatment.				
Medical History and Demographics	Х							
Exam of nasopharynx		X ¹			X ¹	X		
Informed Consent	Х							
ECG monitoring (for the first 20 patients randomized to active treatment)			X ²					
Heart Rate and Blood Pressure Monitoring(for the first 20 patients randomized to active treatment)			X ²					
NIHSS		Х				Х	Х	
Modified Rankin Score (mRS)		Х				Х	Х	
Barthel Index		Х				Х	Х	
FOIS		Х			Х	Х	Х	
DSRS		Х			Х	X	Х	
EQ-5D, EQ-VAS		Х					Х	
Pregnancy Test		X ³						

VFSS	X ⁴		X			
Pneumonia Assessment	X		Х	Χ	X	
Adverse Event (AE) Assessment	Х	Х	X	Х	Х	X
Blinding Assessment					Х	

¹ Assessment of nasopharynx at baseline, 1 week after catheter is in place and at catheter removal using flashlight or pen light. In the event of patient complaint or obvious symotoms, a fiberoptic exam is required and any adverse events are to be reported.

² Rhythm strip (30 seconds) printed at immediately prior to commencing PES treatment, 5 minutes into each of the three treatment sessions, and immediately post treatment. Continual ECG monitoring during PES to observe for any arrhythmias. Heart rate and Blood Pressure to be documented immediately prior to and after PES.

³ Required only for females of child-bearing potential

⁴ Baseline VFSS must meet the threshold criteria of demonstrating a PAS of ≥ 4, in three of the six boli (5 mL/1 tsp/bolus), during swallowing "thin liquid" barium media as assessed by the clinical staff administering the VFSS, unless its considered to be too high risk, then 2 swallows will qualify.

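### The SAP closes the treatment-emergent adverse event window 30 days after a surgery that this trial does not have, while adverse events are collected to the 11-week visit

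*SAP*

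**What the plan says.** SAP 4.9.1 restricts AE analyses to treatment-emergent events, so the definition decides what is tabulated. New-onset events qualify if they are "any adverse event with onset after the administration of study medication through the end of the study, i.e. 30 days after the surgery". The same sentence adds events that were present at baseline and worsened, and events for which the relationship to treatment "was subsequently considered drug-related by the investigator through the end of the study".

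Other parts of the plan set a different horizon:

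- Protocol 8.2.5 collects AEs and serious AEs from consent up to the patient's "study termination and will be assessed for at each encounter with the patient".
- Protocol 5.4: "The length of study participation is approximately 11 weeks, including post treatment follow-up visits at 48 hours", with the last visit at 11 weeks (±1 week).
- Protocol 1.3 and SAP 2.5 (Table 1) both mark an AE assessment in the 11±1 week column. The table header says: "Follow-up timing is based on last Phagenyx treatment".
- Protocol 9.4.4 summarizes related and serious AEs by arm, with no treatment-emergent restriction and no 30-day limit.
- SAP section 5 declares no change from the protocol's analyses.

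**The concern.** The sentence equates the end of the study with a point 30 days after an event that does not occur in this trial. The terms for medication and drug-relatedness in the same sentence do not fit a device trial either, which suggests text carried over from another template.

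By-arm incidence tables are the main safety summary in a trial meant to support a US *de novo* submission. A programmer who applies the clause literally must choose a day to count from. A programmer who ignores it gets a window more than twice as long. The two choices give different tables from the same data, and nothing in the SAP says which is intended. A 30-day cut would also narrow the protocol's safety analysis without being declared.

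**Working it through.** **Is there a surgery to count from?** Protocol 6.1.1 and 6.1.3 describe transnasal catheter placement and three sessions on consecutive days. Surgery appears elsewhere only as background on other therapies (2.2), in an exclusion criterion on altered anatomy (5.2) and in the serious AE text (8.2.2). None of these is a study procedure, so the clause has no anchor.

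**Does another 30-day figure explain it?** Two exist: the loss-to-follow-up rule (protocol 7.2) and the European limit on feeding through the catheter (4.1 and 6.1.1). Neither defines an AE window.

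**Can the SAP's figure be reproduced?** The SAP puts the end of the study at day 30. The inputs for the check are the final visit at 11±1 weeks after the last treatment (SAP Table 1) and three daily sessions, so the first session is 2 days before the last (protocol 6.1.3).

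Follow-up from last treatment = 7 × weeks. Follow-up from first session = 7 × weeks + 2. Days outside the window = follow-up − 30.

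| Final visit | Counted from | Follow-up (days) | Days after day 30 | Share |
|---|---|---|---|---|
| 10 weeks | last treatment | 70 | 70 − 30 = 40 | 57% |
| 11 weeks | last treatment | 77 | 77 − 30 = 47 | 61% |
| 12 weeks | last treatment | 84 | 84 − 30 = 54 | 64% |
| 10 weeks | first session | 72 | 72 − 30 = 42 | 58% |
| 11 weeks | first session | 79 | 79 − 30 = 49 | 62% |
| 12 weeks | first session | 86 | 86 − 30 = 56 | 65% |

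Day 30 is not the end of the study under either anchor. The gap is 40 to 56 days. These are days of follow-up, not events. The documents give no AE rates, so the number of affected events cannot be estimated.

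**The case against.** The strongest reply is that this is leftover wording with little consequence. AE comparisons are descriptive and untested. All on-study AEs are listed, with separate listings of deaths, serious AEs and AEs leading to withdrawal. The serious AE count is not itself labelled treatment-emergent, although the section's opening sentence may restrict it. A sensible programmer might disregard the clause. All of this stands and limits the size of the point. It does not remove it, because listings do not give incidence by arm and the SAP does not say which reading applies.

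Four stronger readings are tempting but not supported:

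- *The sentence sets two different ends.* The later limb repeats the reference to the end of the study without the 30 days. The ordinary reading is one end, wrongly glossed the first time. The real conflict is with protocol 8.2.5 and the schedules.
- *All delayed device effects would drop out of the tables.* If the relatedness limb stands alone and is not confined to events present at baseline, and the end of the study has its plain meaning, late events judged related would still be tabulated. The sentence can be parsed either way.
- *No device exposure remains after the cut-off, so little is lost.* The text "In Europe, patients may receive feeding through the Phagenyx Catheter for up to 30 days" limits feeding, not how long the catheter stays in. Protocol 6.1.4 ties removal after the three treatments to catheters not used for feeding. The exposed time after day 30 cannot be fixed from these passages.
- *Late pneumonia is a separate loss.* The standardized assessment "will be performed over the initial two weeks that patients are enrolled in the study" by protocol design, whatever the SAP window is. For a later case, "If a diagnosis of pneumonia is made, it will be recorded on the AE eCRF" puts it under the same rule as any other AE. If it requires hospitalization it is a serious AE and is listed.

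**Conclusion.** The point holds as a defect in the window definition. SAP 4.9.1 ends the treatment-emergent window at a date that cannot be determined, and it conflicts with the AE follow-up in protocol 8.2.5 and in the SAP's own schedule. Protocol 9.4.4 and SAP section 5 do not rescue it.

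If surgery is read as last treatment, new-onset AEs in 47 of 77 days (40 of 70 to 54 of 84) would be left out of the by-arm treatment-emergent tables. Read as first session, it is 49 of 79 days (42 of 72 to 56 of 86). Both anchors are assumptions, since the documents supply neither. A reader might infer that late safety data would be lost. They would not: the data are collected and listed, and only the tabulation is at risk. Efficacy conclusions do not change. The correction should be made before unblinding, so that the window is not chosen with results in view.

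**What to change.** In SAP 4.9.1:

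1. Delete the clause that places the end of the study 30 days after surgery.
2. Define treatment-emergent as onset or worsening from the first active or sham session through the 11-week visit or study exit.
3. Replace the medication and drug-relatedness terms with device or procedure wording, and make clear whether the relatedness limb applies to any event or only to events present at baseline.
4. State that the serious AE row covers the same follow-up.
5. Reconcile the text with protocol 8.2.5 and 9.4.4. Protocol 9.4.4 has no treatment-emergent restriction, so either align the two or record the restriction in SAP section 5.

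The cost is SAP wording and table shells. No extra data are needed, because AEs are already collected to study termination. Reported AE counts may be higher than under a 30-day cut; the documents give no rates to say by how much.
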